##### **Pre-Vaccination**

- Abbreviated Medical History and Targeted Physical Exam by a study physician or other qualified medical professional
- Urine pregnancy test for female participants of child-bearing potential who do not self-report as pregnant
- Assessment of concomitant medications
- Vital signs
- Nasal swab (participants enrolled under protocol version 7.0 and 8.0 will not be required to provide a nasal swab) and urine sample collections for assessments defined in [Appendix 3: Schedule of Events](#); no blood will be collected pre-vaccination
- Assessment of AEs
- Diary Review (Dose 1) and Distribution (Dose 2)
- Distribution of epinephrine auto-injectors (2 pack) for participants in the HA/MCD group who did not bring with them or bring expired auto-injectors

Following urine sample collections, participants will receive their second vaccination. Following vaccination, the study participant will be observed for AEs, including examination of the vaccination site, and have vital sign measurements and additional urine and blood samples collected 1-hour post-vaccination and/or 30-60 minutes after the onset of an allergic reaction. Sample collections post vaccination will be based on participant weight, detailed further in the MOP.

During the 90-minute observation period, all AEs will be recorded, and AEs judged by an investigator to constitute an allergic reaction, even if not severe, will be documented on the appropriate eCRFs. In the event of an allergic reaction, occurring more than 1 hour post vaccination, urine and blood samples will be collected, per [Appendix 3: Schedule of Events](#). Sample collections post vaccination will be based on participant weight, detailed further in the MOP.

In the event of a systemic allergic reaction, participants will be treated with rescue medications ([Section 7.4: Rescue Medications](#)) and observed for a minimum of 2 hours after their symptoms resolve. Vital signs will be monitored during a systemic allergic reaction.

To assist study participants and/or their parents/legal guardians in the identification of and steps to take in the event of an allergic reaction after they leave the study site, each participant will be provided with an Anaphylaxis Emergency Care Plan. The PI or designee shall review the symptoms and steps to take in the event of an allergic reaction, including training on how to use the epinephrine auto-injector, with the participant and/or parents/legal guardians prior to discharge

#### **9.5.4. Follow-Up Call (Day 32 or 39 ± 1 Day)**

Following their Second Vaccination Visit, participants randomized to placebo, will have a follow-up call, approximately 3 days later. The study team will call the participant to assess for AEs and review the participant diary. Any reported AEs and changes in concomitant medications will be recorded on the appropriate eCRF.

#### **9.6. End of Study Call (Day 29/36 ± 1 Day [No Placebo] or Day 36/43± 1 Day [Placebo]**

All participants who complete their assigned vaccination regimen will complete an End of Study Visit approximately 7 days after their last vaccination. This visit will be conducted over the phone, and participants will be asked to report any new AEs and review their final participant diary.

#### **9.7. Unscheduled Visits**

If a participant develops symptoms of a reaction post-visit or other concerns arise between regularly scheduled visits, participants will be instructed to contact study personnel and may be asked to return to the study site for an “unscheduled” visit. If the participant presents with symptoms for a suspected allergic reaction, the investigator—at his/her discretion, may elect to collect blood samples for the assessment of serum biomarkers and/or complement activation. Additional procedures, including the collection of samples for local labs, will follow the investigator’s elected standard of care.

#### **9.8. Visit Windows**

Study visits should take place within the time limits specified above; the designated visit windows (*i.e. +/- n days*) for each scheduled visit are also indicated in [Appendix 3: Schedule of Events](#). If study visits are not conducted within the visit windows, a protocol deviation will be recorded. In the rare event a vaccination window cannot be met, vaccination may be scheduled beyond the +14-day window. If a participant becomes infected with SARS-CoV-2 or another acute illness following his/her first dose of vaccine, the second vaccination will be delivered, with allowance for a delay up to 90 days following the first dose.

### **10. Mechanistic Assays**

The need for, and extent of, laboratory analysis of systemic allergic reactions will be determined based on the number and character of reactions seen within the trial. Samples will be collected prospectively and stored at a sample repository, with the exception of serum tryptase samples which will be analyzed in “real-time” for those who experience systemic allergic reactions. Specimen collection will be focused on:

- Overall atopic status
- Pre-existing antibodies to polyethylene glycols (Sample analysis will not be completed prior to vaccination; therefore, results will not be used to assess eligibility.)
- Known mediators of systemic reactions due to mast cell activation (e.g., serum tryptase and urinary leukotrienes)
- General markers of an acute inflammatory response (e.g., serum IL-6)

- Activation of the classical and alternative complement pathways
- Contact activation of the kinin system
- Genetic analysis (protocol versions 1.0 – 4.0 only)
- Unsupervised proteomics (blood and urine) and whole blood transcriptomics
- Analysis of peripheral blood mononuclear cells (PBMCs) may also be explored to assess for new mechanisms (e.g., Cellular Indexing of Transcriptomes and Epitopes by Sequencing [CITE-seq] or B cell studies)

Specific anticipated laboratory studies may include, but will not be limited to, those listed below. Specific assays may be removed or added based on the number and character of reactions seen within the trial. In addition, the timepoints for the conduct of specific laboratory studies may change from what is specified below, although the timepoints for sample collection are not anticipated to change.

#### **10.1. Anticipated laboratory studies, protocol versions 1.0 -4.0:**

- Whole blood for genetic analysis: Visit 1, pre-vaccination
- Total IgE: Visit 1, pre-vaccination
- Allergen-specific IgE: Visit 1, pre-vaccination
- Anti-Polyethylene glycol (PEG) IgE, IgG, and IgM antibody measurements: all Visits, pre-vaccination
- Anti-SARS-CoV-2 spike antibodies: all Visits, pre-vaccination
- Serum tryptase: all Visits, pre- and post-vaccination at 1 hour and/or 30-60 minutes after onset of an allergic reaction, including if this occurs after the 1-hour blood draw, and at time of discharge after an allergic reaction
- Serum IL-6: all visits pre- and post-vaccination at 1 hour and/or 30-60 minutes after onset of an allergic reaction including if this occurs after the 1-hour blood draw, and at time of discharge after an allergic reaction
- Complement activation testing: all Visits, pre- and post-vaccination at 1 hour and/or 30-60 minutes after onset of an allergic reaction including if this occurs after the 1-hour blood draw, and at time of discharge after an allergic reaction
- Urinary LTE4: all Visits, pre- and post-vaccination at 1 hour and/or 30-60 minutes after onset of an allergic reaction, including if this occurs after the 1-hour specimen, and at time of discharge after an allergic reaction
- CBC with differential: all Visits, pre- and post-vaccination at 1 hour and/or 30-60 minutes after onset of an allergic reaction, including if this occurs after the 1-hour blood draw, and at time of discharge after an allergic reaction
- Whole blood transcriptomics: all Visits, pre- and post-vaccination at 1 hour and/or 30-60 minutes after onset of an allergic reaction, including if this occurs after the 1-hour blood draw, and at time of discharge after an allergic reaction
- Plasma proteomics: all Visits, pre- and post-vaccination at 1 hour and/or 30-60 minutes after onset of an allergic reaction, including if this occurs after the 1-hour blood draw, and at time of discharge after an allergic reaction
- Urine proteomics: all Visits, pre- and post-vaccination at 1 hour and/or 30-60 minutes after onset of an allergic reaction, including if this occurs after the 1-hour blood draw, and at time of discharge after an allergic reaction
- PBMC separation and storage (only at a sub-set of sites): all Visits, pre-vaccination, and 30-60 minutes after the onset of an allergic reaction, including if this occurs after the 1-hour blood draw. PBMCs will be collected on a sub-set of participants who don't have allergic reactions at the 1-hour time point post-vaccination to serve as controls.) Participants weighing less than 50 kg will not participate in PBMC collections.
- Plasma kallikrein: 30-60 minutes after onset of an allergic reaction, including if this occurs after the 1-hour blood draw, and at time of discharge after an allergic reaction

Details of the laboratory processes are described in Standard Operating Procedures (SOPs) maintained by each laboratory.

#### 10.2. Anticipated laboratory studies protocol version 5.0 – 8.0:

- Total IgE (Visit 1, pre-vaccination)
- Allergen-specific IgE (Visit 1, pre-vaccination)
- Anti-Polyethylene glycol (PEG) IgE, IgG, and IgM antibody measurements: Pre-vaccination at Visit 1 and post-vaccination 1 hour and/or 30-60 minutes after onset of an allergic reaction at each participant's second active vaccination visit
- Anti-SARS-CoV-2 spike antibodies: pre-vaccination at Visit 1 and post-vaccination 1 hour and/or 30-60 minutes after onset of an allergic reaction at each participant's second active vaccination visit
- Serum tryptase: pre-vaccination at Visit 1, all visits post-vaccination 30-60 minutes after onset of an allergic reaction, and 1 hour post-vaccination at each participant's second active vaccination visit
- Serum IL-6: pre-vaccination at Visit 1, all visits post-vaccination 30-60 minutes after onset of an allergic reaction, and 1 hour post-vaccination at each participant's second active vaccination visit
- Complement activation testing: pre-vaccination at Visit 1, all visits post-vaccination 30-60 minutes after onset of an allergic reaction, and 1 hour post-vaccination at each participant's second active vaccination visit
- Urinary LTE4: all Visits, pre- and post-vaccination at 1 hour and/or 30-60 minutes after onset of an allergic reaction, including if this occurs after the 1-hour specimen
- CBC with differential: pre-vaccination at Visit 1, all visits post-vaccination 30-60 minutes after onset of an allergic reaction, and 1 hour post-vaccination at each participant's second active vaccination visit
- Whole blood transcriptomics: pre-vaccination at Visit 1, all visits post-vaccination 30-60 minutes after onset of an allergic reaction, and 1 hour post-vaccination at each participant's second active vaccination visit
- Plasma proteomics: pre-vaccination at Visit 1, all visits post-vaccination 30-60 minutes after onset of an allergic reaction, and 1 hour post-vaccination at each participant's second active vaccination visit
- Urine proteomics: all Visits, pre- and post-vaccination at 1 hour and/or 30-60 minutes after onset of an allergic reaction, including if this occurs after the 1-hour blood draw
- PBMC separation and storage (only at a sub-set of sites for participants weighing greater than 50 kg): pre-vaccination at Visit 1, all visits post-vaccination 30-60 minutes after onset of an allergic reaction, and 1 hour post-vaccination at each participant's second active vaccination visit
- Plasma kallikrein: 30-60 minutes after onset of an allergic reaction, including if this occurs after the 1-hour blood draw after an allergic reaction and 1 hour post-vaccination at each participant's second active vaccination visit

Details of the laboratory processes are described in Standard Operating Procedures (SOPs) maintained by each laboratory.

#### 11. Biospecimen Storage

During the consent process, participants will be asked to give permission for long-term storage and future use of samples for research related to vaccine reactions or allergy research. The following biospecimens and any derivatives will be stored:

- Whole blood (DNA and RNA)
- Serum
- Plasma

- Urine
- PBMCs

Instructions for sample preparation, handling, storage, and shipping are included in the MOP. Site investigators will be responsible for being aware of and observing all the regulations for classification, packaging and labeling, permits or authorizations, and personnel training for shipment of biological and hazardous materials required for the conduct of this study.

## **12. Criteria for Participant and Study Completion and Premature Study Termination**

### **12.1. Participant Completion**

Participation will be considered to be complete when the 7-day follow up after the last vaccination is complete.

### **12.2. Participant Stopping Rules and Withdrawal Criteria**

Participants may be prematurely terminated from the study for the following reasons:

1. The participant and/or parent/legal guardian elects to withdraw consent/assent from all future study activities, including follow-up.
2. The participant is “lost to follow-up” (i.e., no further follow-up is possible because attempts to reestablish contact with the participant have failed).
3. The participant dies.
4. Participants for whom vaccinations are terminated early (refer to [Section 6.5 Premature Discontinuation of Investigational Agent](#)).
5. The Investigator no longer believes participation is in the best interest of the participant.

### **12.3. Participant Replacement**

Participants who withdraw or are withdrawn will not be replaced if they have received at least one vaccine (or placebo) dose. If a participant is randomized but does not receive the first dose of vaccine (or placebo), the participant will be withdrawn and will not be counted toward the total enrollment goal. Additional participants will be randomized to achieve enrollment goals.

### **12.4. Follow-up After Early Study Withdrawal**

Participants who prematurely withdraw (without withdrawing consent) or who are withdrawn may be asked to complete a final phone visit to assess any AEs and concomitant medications as applicable depending on when they are withdrawn relative to the visit schedule. This visit will occur 7 days after the participant received their last vaccine dose. Participants who are withdrawn due to early vaccine termination will be asked to complete study procedures as noted in [Section 6.5 Premature Discontinuation of Investigational Agent](#) prior to being withdrawn from the study. Participants who are withdrawn from the study prior to receipt of study treatment will not be followed after their last completed study visit. Monitoring of a pregnant participant will continue until the conclusion of the pregnancy.

### **12.5. Study Stopping Rules**

Study enrollment will be suspended and vaccinations will be put on hold pending DSMB expedited review of all pertinent data in the event of any one of the following:

1. One Grade 4 or higher AE that is at least possibly related to the vaccine

2. Five participants in the first 100 HA/MCD participants vaccinated or 5% of HA/MCD participants thereafter experience a Grade 3 systemic allergic reaction at least possibly related to the vaccine

Following their unblinded review, the DSMB will determine whether modifications should be made to study conduct and whether and when enrollment and vaccinations can resume.

The study may be suspended or terminated by DAIT/NIAID or the DSMB upon review of any observations, events, or new information that merits such action. In the case of suspension or premature termination, DAIT/NIAID will promptly inform the investigators and regulatory authorities as appropriate of the suspension or termination and the reason for suspension/termination.

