## 1.3. Clinical Studies

Overall, 15,419 participants aged 18 years or older received at least one dose of the Moderna COVID-19 Vaccine in three clinical trials. Adverse reactions reported in a clinical trial following administration of the Moderna COVID-19 Vaccine include pain at the injection site, fatigue, headache, myalgia, arthralgia, chills, nausea/vomiting, axillary swelling/tenderness, fever, swelling at the injection site, and erythema at the injection site. A phase 2/3, randomized, observer-blind, placebo-controlled study to evaluate the safety, reactogenicity, and effectiveness of the same 100 mcg dose of Moderna COVID-19 Vaccine used in adults is currently ongoing in approximately 3,000 healthy adolescents 12 to < 18 years of age (NCT04649151), as is a variable dose study in children 6 months to < 12 years (NCT04796896).

The safety of the Pfizer-BioNTech COVID-19 Vaccine has been evaluated in three clinical studies. The BNT162-01 study (NCT04380701) was a phase 1/2 trial that enrolled 60 participants, 18 through 55 years of age. Study C459001 is an ongoing phase 1/2/3 study that has enrolled approximately 44,000 participants, 12 years of age or older.

Study C4591007 (Study 3) is a Phase 1/2/3 multicenter, randomized, dose-finding, open-label (Phase 1) and multinational, saline placebo-controlled, observer-blind, immunogenicity and efficacy (Phase 2/3) study that has enrolled 4,695 participants 5 through 11 years of age, of whom 3109 participants received Pfizer-BioNTech COVID-19

Vaccine (10 mcg modRNA) and 1538 participants received placebo in Phase 2/3. In an analysis of Study 3 Phase 2/3 data based on data up to the cutoff date of September 06, 2021, 2,268 participants [1,518 Pfizer-BioNTech COVID-19 Vaccine (10 mcg modRNA); 750 placebo] were 5 through 11 years of age. Of these, 2,158 (95.1%) [1,444 Pfizer-BioNTech COVID-19 Vaccine (10 mcg modRNA) and 714 placebo] participants have been followed for at least 2 months after the second dose. An analysis of Study 3 Phase 2/3 adverse event data also included another 2,379 participants [1,591 Pfizer-BioNTech COVID-19 Vaccine (10 mcg modRNA) and 788 placebo], of whom 71.2% had a follow-up period for at least 2 weeks after Dose 2 up to the cutoff date of October 8, 2021. The safety evaluation in Study 3 is ongoing.

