As the pandemic has continued, the emergency use approvals have been expanded to younger ages over time. To date, the enrollment in DAIT-COVID-19-004 has been very largely adults. To ascertain if age is a risk factor for reaction, beginning under protocol version 5.0, children aged 5 to 17 years will be enrolled. The Pfizer-BioNTech COVID-19 Vaccine is currently approved for individuals 5 to 15 years of age under EUA and 16 years or older under full licensure. A phase 2/3 study is currently underway for the Moderna COVID-19 Vaccine in children from age 6 months to age 11 years ([Section 1.3](#)). Both because school aged children have not been assessed for the incidence of systemic allergic reactions to the mRNA vaccines and because they have a higher rate of food allergy-induced anaphylaxis than adults, it is important to include them in the assessment of reactions.

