### **6.5. Premature Discontinuation of Investigational Agent**

Vaccination will be prematurely discontinued for any participant for any of the following reasons:

- Participant has a CoFAR Grade 2 or higher systemic allergic reaction regardless of tryptase, or a CoFAR Grade 1 reaction with elevated tryptase [1.2 x baseline plus 2 ng/ml] that is at least possibly related to the first dose of the vaccine. If the systemic allergic reaction took place after the participant has left the vaccination clinic and no tryptase measurements are available, Grade 1 events will not constitute criteria for discontinuation, but counseling by a study physician will be required (see below).
- The investigator believes that it is no longer in the best interest of the participant to receive the second vaccination

In the above cases, the participant will be asked to return for his/her next in clinic study visit during which reactogenicity symptoms will be reviewed (electronic diary review or return and review of paper diary), adverse events (AEs) and concomitant medications will be recorded, and pre-vaccination biospecimens will be obtained per protocol.

Vaccination may be prematurely discontinued for any participant for any of the following reasons:

- If a participant has a Grade 1 (per [CoFAR Grading Scale](#)) systemic allergic reaction with no evidence of systemic mast cell activation to the first dose of either the Pfizer-BioNTech COVID-19 Vaccine or Moderna COVID-19 Vaccine, he/she will receive counseling by a study physician and will be allowed to receive a second dose if he/she so chooses.
- Because the placebo will consist of a normal saline injection, a reaction to placebo will not require termination from subsequent active vaccination, if the participant is willing to proceed following counseling.
- If a participant becomes pregnant between the first and second doses of vaccine, she will receive counseling by a study physician and will be allowed to receive a second dose if she so chooses.

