## **13.8. Review of Safety Information**

### **13.8.1. Medical Monitor Review**

The DAIT/NIAID Medical Monitor shall receive reports (approximately every two weeks) from the SACC compiling new and accumulating information on AEs, SAEs, and pregnancies recorded by the study site(s) on appropriate eCRFs.

In addition, the DAIT/NIAID Medical Monitor shall review and make decisions on the disposition of the SAE and pregnancy reports received by the SACC (See [Section 13.5.1 Reporting of Serious Adverse Events to DAIT/NIAID](#) and [Section 12.6 Pregnancy Reporting](#)).

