### **13.8.2. DSMB Review**

#### **13.8.2.1. Planned DSMB Reviews**

The NIAID Allergy and Asthma Data and Safety Monitoring Board (DSMB) shall review unblinded outcome and safety data after approximately every 500 participants complete their vaccination schedule. Unblinded data for the planned safety reviews will include, at a minimum, a listing of all reported AEs and SAEs by vaccine arm/placebo and population. Outcome data will show the counts, proportions (with corresponding 95% CI), and difference in proportions between the HA/MCD and comparison group within each vaccine (with corresponding 95% CI) of the primary and key secondary endpoints. Interim p-values will be available upon request. Data may be reviewed and discussed via email or by teleconference. The DSMB may recommend continuing the study, modifying the study, stopping the study, and/or announcing information will the study is still ongoing.

The DSMB will also review results of the planned interim analysis of the primary endpoint (Refer to [Section 14.5.1 Interim Analysis of Primary Endpoint](#)). In addition to reviewing interim analysis results, the DSMB will be asked to consider the nature and severity of the reactions, the rate of reactions in the placebo arm, and the adequacy of information obtained that will allow in-depth characterization of the risk and nature of systemic allergic reactions in the HA/MCD population. The DSMB may recommend continuing the study, modifying the study, or stopping the study. DAIT/NIAID, as sponsor, will determine whether any changes to study conduct will be implemented.

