#### **13.8.2.2. *Ad hoc* DSMB Safety Reviews**

In addition to the pre-scheduled data reviews and planned safety monitoring, the DSMB may be called upon for *ad hoc* reviews. The DSMB will review any event that potentially impacts safety at the request

of the protocol chair or DAIT/NIAID Medical Monitor. The DAIT/NIAID Medical Monitor will inform the DSMB of an Expedited Safety Report within 24-48 hours.

In addition, an *ad hoc* comprehensive DSMB Safety Review will be triggered in the event that a study stopping rule is met ([Section 12.5 Study Stopping Rules](#)).

After review of the unblinded data, the DSMB will make recommendations regarding study conduct, including modifications and/or continuation. The DSMB will recommend and DAIT/NIAID, as Sponsor, will determine whether protocol changes should be implemented and/or whether and when enrollment and vaccinations can resume.

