#### **13.8.2.2.1. Temporary Suspension of Enrollment and Vaccinations for *ad hoc* DSMB Safety Review**

A temporary halt in enrollment will be implemented by the Sponsor if an *ad hoc* DSMB safety review is required. New participants will not be consented for study participation during the enrollment halt. All vaccinations will be placed on hold. Participants screened but not yet randomized will not be allowed to continue with the Enrollment Visit. All participants not randomized within 7 days of screening must be rescreened.

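### Stopping rule 2 counts HA/MCD participants study-wide, so earlier, largely adult enrolment dilutes its automatic 5% Grade 3 hold for the 5–17 cohort

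*Protocol*

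**What the plan says.** Rule 2 is worded alike in Protocol 12.5, the Protocol Synopsis and the SAP synopsis: "Five participants in the first 100 HA/MCD participants vaccinated or 5% of HA/MCD participants thereafter experience a Grade 3 systemic allergic reaction". Only reactions judged possibly or definitely vaccine-related count. If it is met, enrolment and vaccination stop until an expedited DSMB review. HA/MCD is its only population term.

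Versions 1.0–4.0 took participants aged 12 and over. Versions 5.0–8.0 take only ages 5–17. Protocol 4.1 says that up to that change "the enrollment in DAIT-COVID-19-004 has been very largely adults". Protocol 14.7 plans 300 children per vaccine, 180 of them HA/MCD.

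Other provisions bear on the same events:

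- **Individual discontinuation (Protocol 6.5).** Vaccination stops for that person if "Participant has a CoFAR Grade 2 or higher systemic allergic reaction regardless of tryptase" and the reaction is at least possibly related to the first dose.
- **Rule 1 and discretion (Protocol 12.5).** One related adverse event of Grade 4 or higher triggers the hold. The sponsor or DSMB may also suspend the study on any new information.
- **Medical monitor (Protocol 13.8.1).** The monitor "shall receive reports (approximately every two weeks) from the SACC compiling new and accumulating information" on adverse events.
- **Scheduled DSMB review (Protocol 13.8.2.1).** The DSMB "shall review unblinded outcome and safety data after approximately every 500 participants complete their vaccination schedule".
- **Ad hoc DSMB review.** Under Protocol 13.8.2.2 a "comprehensive DSMB Safety Review will be triggered in the event that a study stopping rule is met". SAP 10 goes further and requires DSMB review of any event that could contribute to a stopping rule. Protocol 13.8.2.2.1 says "A temporary halt in enrollment will be implemented by the Sponsor" when an ad hoc review is required, with all vaccinations held.

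**The concern.** Children were added partly to learn whether age is a risk factor. Protocol 4.1 says the incidence of systemic allergic reactions in school-aged children has not been assessed. The protocol gives children their own sample size and precision, and SAP 8.1 gives them separate safety displays. The stopping rule was not adapted in the same way.

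Once 100 HA/MCD participants have been vaccinated under earlier versions, the first limb of rule 2 is used up before any version 5.0 child is exposed. The 5% limb then carries the earlier participants in its denominator. It no longer acts at 5% in the group now receiving vaccine.

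At stake is the one automatic, pre-set Grade 3 hold. General safety data in children do exist: Protocol 1.3 describes a study that enrolled "4,695 participants 5 through 11 years of age, of whom 3109 participants received Pfizer-BioNTech COVID-19" vaccine. The concern is therefore confined to allergic reactions in the HA/MCD child group.

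**Working it through.** **The plan's own figures.** The documents give no operating characteristics for rule 2. The child precision statement in Protocol 14.7 does reproduce: for 0 of 180 the exact upper limit is 1 − 0.025^(1/180) = 0.020. For 0 of 1020 it is 0.0036. Both match.

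**Inputs.** HA/MCD children: 180 (Protocol 14.7). Threshold: 5 in the first 100, then 5% (Protocol 12.5). Earlier HA/MCD participants, M: not stated, so assumed from 100 to 500. Earlier Grade 3 events, e: assumed 0, then 1%.

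**Child reactions needed at child k.**

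- Pooled count: ceil(0.05 × (M + k)) − e.
- Pooled count, if *thereafter* drops the first 100 from the denominator: ceil(0.05 × (M − 100 + k)) − e, where e then counts only events after the first 100.
- Child-only count: 5 for k ≤ 100, then ceil(0.05 × k).

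At k = 180 with e = 0, the child-only count needs 9. The pooled count with M = 500 needs 0.05 × 680 = 34, or 0.05 × 580 = 29 if the first 100 are dropped.

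**Chance that rule 2 fires by child 180.** This is an exact binomial recursion, checking the rule after each child, with e = 0.

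| Count | Needed at child 180 | True Grade 3 rate 5% | True Grade 3 rate 10% |
|---|---|---|---|
| Child-only | 9 | 71% | 99.8% |
| Pooled, M = 100 | 14 | 10% | 89% |
| Pooled, M = 200 | 19 | 0.2% | 45% |
| Pooled, M = 300 | 24 | about 0 | 9% |
| Pooled, M = 500 | 34 | about 0 | 0.02% |
| First 100 dropped, M = 200 | 14 | 10% | 89% |
| First 100 dropped, M = 300 | 19 | 0.2% | 45% |
| First 100 dropped, M = 500 | 29 | about 0 | 0.7% |

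With the first 100 dropped and M = 100 there is no dilution.

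**Earlier events.** If 1% of earlier participants reacted, the pooled figures at a 10% child rate become 94%, 66%, 27% and 0.7% for M = 100, 200, 300 and 500. With the first 100 dropped they become 94%, 66% and 6% for M = 200, 300 and 500.

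**False pauses under a child-only count.** The chance of firing is 0.4% at a true 1% Grade 3 rate and 6% at 2%.

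**Single-event review under SAP 10.** The chance of at least one Grade 3 reaction among n children is 1 − (1 − p)^n. At p = 5% it is 1 − 0.95^45 = 90% by child 45 and over 99.9% by child 180. At p = 10% it is 1 − 0.90^22 = 90% by child 22.

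**Scheduled reviews.** They fall about every 500 completers and the child goal is 300 per vaccine, so none is guaranteed within the child cohort.

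**The case against.** The strongest reply is SAP 10. A related Grade 3 reaction in an HA/MCD child is an event that could contribute to rule 2, so it must go to the DSMB. That route has no denominator and earlier participants cannot dilute it. As shown above, it would probably bring child data to the DSMB sooner than a count needing five events. Protocol 13.8.2.2.1 can also be read as holding vaccination whenever an ad hoc review is required. This stands, and it limits the consequence.

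It does not settle the matter. Protocol 13.8.2.2 ties the automatic comprehensive review to a rule being met, and a hold at every single Grade 3 event would leave rule 2 largely redundant. Whether a SAP 10 review brings the hold is therefore unclear. If it does not, a pause depends on case-by-case judgement. Rule 1 needs a Grade 4 event, and withholding dose 2 protects only the child who has already reacted.

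Three further replies are fair. Earlier enrolment is unknown. The rates at issue are high: the protocol plans for 1% in HA/MCD, and 5% as detectable in children, for any qualifying reaction rather than Grade 3 alone. And the sponsor set 5% for HA/MCD as a whole, not for each subgroup, so a child count is a design choice rather than the repair of a stated promise.

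A reader might infer that the fall from 99.8% to 0.02% measures lost protection, or that children have no effective stopping safeguard. The documents support neither. The figures describe only whether rule 2 fires. They leave out SAP 10 review, rule 1 and discretionary suspension.

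**Conclusion.** The point holds as the loss of an automatic hold. Under either reading of *thereafter*, rule 2 loses most of its ability to fire for the 5–17 cohort once about 300 to 500 earlier HA/MCD participants are counted. At M = 100 and a 10% rate the loss is small to modest, or nil if the first 100 are dropped.

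This rests on at least 100 HA/MCD participants having been vaccinated before version 5.0, on an earlier Grade 3 rate well below 5%, and on 180 HA/MCD children with a common, independent reaction risk. It matters only if children react at Grade 3 rates near or above 5%. At a true 1% rate neither count is expected to fire. It is worth fixing because the change is cheap and concerns participant safety. Confidence is medium, because earlier enrolment is not given and the reach of the hold in 13.8.2.2.1 is ambiguous.

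**What to change.** In Protocol 12.5 and both synopses, add: *Rule 2 is also applied to a separate count of participants enrolled under versions 5.0–8.0: five of the first 100 HA/MCD participants vaccinated in that cohort, then 5% of all HA/MCD participants vaccinated in it.* In Protocol 13.8.2.2.1, state whether the hold applies to DSMB reviews of single events under SAP 10.

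Two additions are optional. One is a scheduled DSMB review within the child cohort, for example after 100 HA/MCD children, with child data shown separately. The other is to restart the child count if the active vaccine changes to Moderna.

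The cost is amendment wording and one extra running count, plus one DSMB report if the optional review is adopted. SAP 8.1 already splits safety displays by adult and child. The downside is a temporary false pause, at the 0.4% and 6% rates given above. With the Moderna restart and a second 180 HA/MCD children, these become 1 − (1 − 0.0039)² = 0.8% at a true 1% rate and 1 − (1 − 0.0635)² = 12% at 2%.
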